## 7. Statistical Analysis

### 7.1. Sample size calculation

Response to treatment with biologics is estimated at 50%, meaning that half of included patients are expected to be non-responders. Considering a minimal sample of 10 patients that present the event of interest per independent variable included in the logistic regression model and a maximum of 10 independent variables per model, a minimum estimated sample of 200 UC patients and 200 CD patients is required.

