4. STUDY POPULATIONS

4.1. Definition of study populations to analyse

Study Population: All patients who meet the selection criteria and have given their informed consent will be included in the analysis.

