7.2. Primary efficacy endpoint

- **Primary endpoint:** Evaluate the impact of the co-morbidities profile in IBD patients on treatment response to biological therapy.

The analysis that will be performed to answer the objective will be the following:

In order to determine the level of correlation between the co-morbidities profile and treatment response, adjusting for sociodemographic and clinical profile of patients, two logistic regression models will be conducted. The dependent variable of the models will be the **lack of response during the induction phase and the loss of response during the maintenance phase**. In both models independent variables will include all comorbidities, as well as sociodemographic and clinical variables as covariates.

- The following potential variables will be considered for the analysis:
 - Crohn's Disease or Ulcerative Colitis.
 - Myocardial Infarction (yes/no).
 - Congestive Heart Failure (yes/no).
 - Peripheral Vascular Disease (yes/no).
 - Cerebrovascular Disease (yes/no).
 - Dementia (yes/no).
 - Chronic Obstructive Pulmonary Disease (yes/no).
 - Connective Tissue Disease (yes/no).
 - Peptic Ulcer Disease (yes/no).
 - Mild Chronic Hepatopathy (yes/no).
 - Diabetes Mellitus (yes/no).
 - Hemiplegic (yes/no).
 - Moderate-Severe Chronic Kidney Disease (yes/no).
 - Diabetes with lesions in target organs (yes/no).
 - Solid Tumor (yes/no).
 - Leukemia (yes/no).
 - Lymphoma (yes/no).

- Moderate-Severe Chronic Hepatopathy (yes/no).
 - Solid tumor with metastases (yes/no)
 - Acquired immunodeficiency syndrome (AIDS) (yes/no).
 - Gender.
 - Race (caucasian, asiatic, latin, black, other).
 - Level of education (uneducated, primary education, secondary education, university education).
 - Working status (student, self-employed, employed by other, retired, housework, unemployed, temporarily unable to work, permanently unable to work, other).
 - Smoking habits (non-smoker, ex-smoker and smoker).
 - Alcohol abuse (yes/no).
 - Time from diagnostic of disease.
 - Disease location.
 - Discontinuation the biological treatment (yes/no)
- Each one of the variables will be compared between the subjects with primary non-response vs primary response and primary response maintenance vs loss of response and those variables whose p-value is lower than 0.1 are considered potential variables for performing a logistic regression analysis.

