 - For the comparison of the variables between subjects, the following criteria will be considered: dichotomous or categorical variables will be compared between the two groups using the Chi-squared test. Continuous variables will be compared between the two groups using the Student's T-test for independent samples.
- The logistic regression models will be assessed and the results will be submitted for any statistically significant model, providing the following results: Odds Ratio, 95%CI, p-value, sensitivity and specificity. The models will be assessed using stepwise automatic variable Wald entry (backward and forward) techniques and entry also assessing the specificity and sensitivity of the final model.

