- Non severe (Remission <5; Mild disease 5-7; Moderate disease 8-16)
- Severe disease >16

Partial Mayo Index Score

- Non severe (Remission = 0-1; Mild Disease = 2-4; Moderate Disease = 5-7)
- Severe Disease =8-9

We will compare the percentage of patients reporting each co-morbidity between IBP severe or non-severe using Chi-Square.

A logistic regression analysis will be performed, in which **IBP severe or non-severe at baseline** will be used as the dependent variable and patient disease (CD or UC) and different comorbidities variables will be used as independent variables, yielding the following results: Odds Ratio, 95%CI, p-value, sensitivity and specificity.

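### The sensitivity and specificity of the final models are measured in the patients used to select and fit them, with no validation and no stated cut-off, so they are biased upwards

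*SAP*

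**What the plan says.** SAP 7.2 plans two logistic regressions, one for primary non-response and one for loss of response. The list introduced by "The following potential variables will be considered for the analysis" has 29 entries. Each entry is compared between outcome groups, and "those variables whose p-value is lower than 0.1 are considered potential variables for performing a logistic regression analysis". The survivors go through "stepwise automatic variable Wald entry (backward and forward) techniques". The same sentence ends with "entry also assessing the specificity and sensitivity of the final model". Section 7.2 also says that "the results will be submitted for any statistically significant model".

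SAP 7.3 promises "Odds Ratio, 95%CI, p-value, sensitivity and specificity" for two further analyses: response on the extraintestinal manifestations, and baseline severity on the comorbidities. It describes no screening or stepwise step for either.

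The analysis set is the same throughout. SAP 4.1 states that "All patients who meet the selection criteria and have given their informed consent will be included in the analysis", and every regression table in SAP Appendix 1 names that study population. Neither document mentions a hold-out set, cross-validation, a bootstrap, an optimism correction or an external sample. No probability cut-off is given, and no entry or removal p-values.

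**The concern.** Sensitivity and specificity judge how well a model classifies patients. If the patients who decide which variables enter also grade the result, variables that fit by chance are chosen and then credited for that fit. Even without selection, coefficients fitted to a sample classify that sample better than they classify new patients.

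This is more than incidental output, because the last paragraph of Protocol section 4 gives as an aim a comorbidity scale to predict response to biologics. A reader would judge such a scale by its stated sensitivity and specificity.

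**Working it through.** **The plan's own figure.** Protocol 7.1 says "Response to treatment with biologics is estimated at 50"%, and assumes 10 events per variable and at most 10 variables. So n = 10 × 10 / 0.50 = 200 per disease, as stated, and 400 in all. Disease type is a candidate in SAP 7.2, so the models there pool the two diseases. Loss of response is defined in initial responders (Protocol 6.4.5), so that model may use fewer patients: 400 × 0.50 = 200 on the sizing assumption, or 400 × 0.70 = 280 if 30% are primary non-responders, the upper figure in Protocol section 4.

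**Candidates.** 1 (disease type) + 19 (comorbidities) + 9 (gender, race, education, working status, smoking, alcohol, time from diagnosis, location, discontinuation) = 29.

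**Chance selection, 29 independent null candidates.**
- At p<0.1: 29 × 0.1 = 2.9 expected; P(at least one) = 1 − 0.9^29 = 0.953.
- At p<0.05: 29 × 0.05 = 1.45 expected; P(at least one) = 1 − 0.95^29 = 0.774.

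**Simulation of SAP 7.2 with no true predictor.** There were 400 data sets per setting: screening by chi-squared or t-test at p<0.1, then forward selection (entry 0.05, removal 0.10) or backward elimination (removal 0.10). Performance was measured in the same patients and in 4,000 new ones. Thresholds and prevalences are assumptions, because the documents give none. The settings below have 50% events and a cut-off of 0.5, which here equals the event rate.

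| Comorbidity prevalence | n | Method | Any model retained | Apparent AUC | Apparent sens + spec | New patients |
|---|---|---|---|---|---|---|
| 0.5-5% | 400 | forward | 63% | 0.559 | 1.09 | 1.00 |
| 0.5-5% | 400 | backward | 89% | 0.567 | 1.10 | 1.00 |
| 5-20% | 400 | forward | 72% | 0.575 | 1.11 | 1.00 |
| 5-20% | 400 | backward | 94% | 0.587 | 1.13 | 1.00 |
| 0.5-5% | 200 | forward | 42% | 0.577 | 1.12 | 1.00 |
| 0.5-5% | 200 | backward | 71% | 0.591 | 1.14 | 1.00 |
| 5-20% | 200 | forward | 64% | 0.596 | 1.15 | 1.00 |
| 5-20% | 200 | backward | 93% | 0.610 | 1.16 | 1.00 |

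The Monte Carlo standard error on the model frequency is about √(0.6 × 0.4 / 400) = 2.4 points. The backward rows count any retained model, including one kept only at the looser 0.10 criterion.

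Further runs at 0.5-6% prevalence, with forward entry at 0.05 and the cut-off at the event rate, gave a model in 57-60% of data sets at n=400, with a mean sum of 1.09-1.12. At n=200-280 the mean sum was 1.12-1.18.

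**Upper tail.** The 95th percentile of apparent AUC is 0.63-0.66 at n=400 and 0.67-0.70 at n=200. The 90th percentile of the sum is 1.17-1.19 at n=400 and 1.22-1.26 at n=200-280.

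**Dependence on the cut-off.** At 30% events and a cut-off of 0.5, n=400, the noise model shows sensitivity 0.04-0.06 and specificity 0.98-0.99. The sum is then only about 1.02-1.05 across the runs.

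**SAP 7.3 models, all predictors entered, no true effect, cut-off at the event rate.**
- Extraintestinal manifestations (9 + disease type = 10 predictors): mean sum about 1.09-1.11 at n=400 and 1.11-1.14 at n=200-280.
- Severity (19 comorbidities + disease type = 20 predictors), n=400: about 1.16 if 20% are severe, 1.22 if 10% and 1.29 if 5%.
- New patients: 1.00. At 15-30% events with a cut-off of 0.5, the apparent sums fall to 1.00-1.06.

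Prevalences and the proportion severe are again assumed.

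**The case against.** The strongest reply is that the excess is small. A sum of 1.09-1.13 is roughly 0.55 for each measure, and few readers would call that a useful classifier. A reader might infer that noise passed through this plan will look predictive; the calculations do not support that for the average model. Only the upper tail approaches it, and at 30% events with a 0.5 cut-off the noise model plainly fails. This stands, and it limits the claim to upward bias of modest average size.

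Second, a reader might blame stepwise selection for all of it. SAP 7.3 states no selection step, so optimism there comes from fitting and evaluating in the same patients. The two causes need separate handling, and dropping stepwise selection from 7.2 would not correct 7.3.

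Third, a reader might conclude that a non-significant primary model will never be seen. SAP 7.2 does carry a significance condition, but Appendix 1 plans Tables 14.3.1.2 and 14.3.1.4 for both regressions without one, and Tables 14.3.1.1 and 14.3.1.3 compare the candidates by outcome. This is an inconsistency to settle rather than proof of suppressed results.

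Fourth, SAP 5.1 calls the work descriptive and exploratory, and no SAP analysis builds the scale named in Protocol section 4. That tempers the clinical stakes but does not unbias a reported sensitivity. Nor does the rule in Protocol 7.4 of 10 patients per variable and response category: it limits variables in the model, not the 29 screened, and does not adjust the reported accuracy.

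**Conclusion.** The concern holds in measured form. The direction of bias follows from the design: selection, fitting and evaluation share the same patients, and no correction is planned. If nothing predicts response, a primary model still emerges in roughly 60% of data sets at n=400 with forward entry at 0.05, and in 42-94% across the settings tried. At an event-rate cut-off its sensitivity plus specificity is overstated by about 0.09-0.13 on average at n=400 and by 0.12-0.18 at n=200-280. The excess is larger in the tail and nearly vanishes at 30% events with a 0.5 cut-off. The severity model could be worse than the primary ones if few patients are severe.

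These sizes rest on assumed prevalences, independent candidates, assumed stepwise thresholds and a cut-off that the SAP does not give. The frequency of a chance model is the least stable figure. That so much turns on an unstated cut-off is itself a gap in the plan.

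**What to change.** In SAP 7.2 and 7.3:

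1. State the probability cut-off in advance and, for 7.2, the stepwise entry and removal criteria.
2. Report optimism-corrected AUC, sensitivity and specificity from at least 500 bootstrap samples. Each sample should repeat all screening and selection for the 7.2 models, and the full fit for the 7.3 models.
3. State a rule for comorbidities too rare to estimate in a resample, such as penalised fitting or grouping. At 0.5% prevalence, 400 patients contain about 2 carriers, and a resample contains neither with probability (398/400)^400 ≈ 0.13.
4. Bring the significance condition in 7.2 into line with Appendix 1, so that both planned models are reported whether or not significant.
5. Deal separately with the candidate for discontinuation of the biologic. SAP 6.1 lists primary non-response and loss of response among its reasons, so it is partly a consequence of the outcome. Bootstrap correction cannot remove that inflation.

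No new data are needed. The cost is some programming, and the stated accuracy will be less favourable.

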7.3. Secondary efficacy endpoints

- Secondary endpoint: Evaluate the impact of Extraintestinal Manifestations profile in IBD patients on treatment response to biological therapy.

The analysis that will be performed to answer the objective will be the following:

To evaluate the impact of extraintestinal manifestations profile in IBD patients on treatment response to biological therapy, a logistic regression analysis will be performed, in which **lack of response during the induction phase** will be used as the dependent variable and patient disease (CD or UC) and different extraintestinal manifestations variables (arthropathy and arthritis, metabolic bone disease, eye disease, oral, aural and nasal disease, skin disease, hepato-pancreato-biliary disease, neurological disease, cardiovascular manifestations of IBD,

pulmonary manifestations of IBD) will be used as independent variables, yielding the following results: Odds Ratio, 95%CI, p-value, sensitivity and specificity.

We will repeat this analysis with the **loss of response during the maintenance phase variable** as dependent variable.

- **Secondary endpoint: Describe the percentage of IBD patients exhibiting co-morbidities.**

The analysis that will be performed to answer the objective will be the following:

We will provide the frequencies, percentages and 95%CI of the following comorbidities for patients with Crohn's Disease and Ulcerative Colitis separately:

- Myocardial Infarction (yes/no).
- Congestive Heart Failure (yes/no).
- Peripheral Vascular Disease (yes/no).
- Cerebrovascular Disease (yes/no).
- Dementia (yes/no).
- Chronic Obstructive Pulmonary Disease (yes/no).
- Connective Tissue Disease (yes/no).
- Peptic Ulcer Disease (yes/no).
- Mild Chronic Hepatopathy (yes/no).
- Diabetes Mellitus (yes/no).
- Hemiplegic (yes/no).
- Moderate-Severe Chronic Kidney Disease (yes/no).
- Diabetes with lesions in target organs (yes/no).
- Solid Tumor (yes/no).
- Leukemia (yes/no).
- Lymphoma (yes/no).
- Moderate-Severe Chronic Hepatopathy (yes/no).
- Solid tumor with metastases (yes/no)
- Acquired immunodeficiency syndrome (AIDS) (yes/no).

- **Secondary endpoint: Determine the co-morbidities profile according to the level of IBD severity.**

The analysis that will be performed to answer the objective will be the following:

We will classify the patients into IBD severe or non-severe at baseline based on the HBI and PMI scores according the following criteria:

Harvey-Bradshaw Index score

- Non severe (Remission <5; Mild disease 5-7; Moderate disease 8-16)
- Severe disease >16

Partial Mayo Index Score

- Non severe (Remission = 0-1; Mild Disease = 2-4; Moderate Disease = 5-7)
- Severe Disease =8-9

We will compare the percentage of patients reporting each co-morbidity between IBP severe or non-severe using Chi-Square.

A logistic regression analysis will be performed, in which **IBP severe or non-severe at baseline** will be used as the dependent variable and patient disease (CD or UC) and different comorbidities variables will be used as independent variables, yielding the following results: Odds Ratio, 95%CI, p-value, sensitivity and specificity.

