## 6. Methodology

### 6.1. Study design

In order to meet the objectives of the present study, a retrospective, non-interventional, multicentre observational study including 25 gastroenterology sites from all around Spain has been designed. Participating investigators will be gastroenterologists and will include consecutive patients diagnosed with UC or CD that started treatment with biologics between June 2011 and June 2013, after giving written informed consent. The study will consist of one only visit in which investigators will collect patients' sociodemographic (age, gender, race, level of education, smoking habits alcohol intake) and clinical (concomitant diseases, date of diagnosis, previous treatment, current treatment, disease activity when starting treatment with biologics and at the study visit, current situation in terms of treatment with biologics) data from medical charts or directly from patients (in case of discrepancy, the information coming from medical charts will be preferable). Time since patients started biological treatment until study visit or until lack of treatment response or until treatment change will constitute the reference period for the study. In order to fulfill current legislations regarding non-interventional studies, investigators will commit to follow usual clinical practice.

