#### 6.4.4. Study variables

The following **sociodemographic variables** will be collected from patients' medical records or directly from patients during the study visit, straight after their inclusion in the study:

- Age
- Gender
- Race (caucasian, asiatic, latin, black, other)
- Level of education (uneducated, primary education, secondary education, university education)
- Working status (student, self-employed, employed by other, retired, housework, unemployed, temporarily unable to work, permanently unable to work, other)
- Smoking habits (non-smoker, ex-smoker, smoker, number of cigarettes per day)
- Alcohol intake (units per week).

The following **clinical variables** will be collected from patients' medical records (when available) or directly from patients during the study visit, straight after their inclusion in the study:

- Date of diagnosis (UD or CD).
- Disease activity at the beginning of the reference period and at the study visit through collection of the following variables:
  - For UC patients:
    - Partial Mayo Score (PMS) (9 point scale that excludes the endoscopic appearance of the mucosa)
    - General disease activity:
      - Mild: up to four bloody stools daily and no systemic toxicity
      - Moderate: four to six bloody stools daily and minimal toxicity
      - Severe: more than six bloody stools daily and signs of toxicity, such as fever, tachycardia, anaemia, raised erythrocyte sedimentation rate.
      - Fulminant: More than ten bloody stools daily, continuous bleeding, anaemia requiring blood transfusion, abdominal tenderness and colonic dilatation on plain abdominal radiographs.
    - Disease anatomic extent: proctitis, left-sided colitis or pancolitis.
    - Endoscopy findings:

- Normal or inactive disease
- Mild disease (erythema, decreased vascular pattern, mild friability)
- Moderate disease (marked erythema, lack of vascular pattern, friability erosions)
- Severe disease (spontaneous bleeding, ulceration).
- For CD patients:
  - Harvey-Bradshaw Index (HBI) (a simplified version of CDAI)
  - General disease activity:
    - Mild to moderate: ambulatory patients able to tolerate oral alimentation without manifestations of dehydration, toxicity, abdominal tenderness, painful mass, obstruction or >10% weight loss.

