#### **7.4. Assessment of the primary objective: Evaluate the impact of the co-morbidities profile in IBD patients on treatment response to biological therapy**

In order to determine the level of correlation between the co-morbidities profile and treatment response, adjusting for sociodemographic and clinical profile of patients, two logistic regression models will be conducted. The dependent variable of the models will be the lack of response during the induction phase (primary non response) and the loss of response during the maintenance phase (secondary loss of response) (see section 6.4.6). In both models independent variables will include all comorbidities included in the study, as well as sociodemographic and clinical variables as covariates. The maximum number of independent variables included in the model will be defined according to the number of patients per response category in the dependent variable. The maximum number of variables will be defined to ensure a minimum of 10 patients per independent variable and response category in the dependent one.

Depending on the volume of patients that have discontinued a biological treatment and started treatment with a different biologic during the reference period, this sample may be separately analyzed.

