5.2. Subject Characteristics

The analysis of continuous variables will be described by the mean, median, standard deviation, minimum and maximum. This analysis included the age of patients and number pack-year in smoking habits.

The analysis of categorical variables will be described by the distribution of frequencies and percentages.

This analysis included the following variables:

- Gender.
- Race (caucasian, asiatic, latin, black, other).
- Level of education (uneducated, primary education, secondary education, university education).
- Working status (student, self-employed, employed by other, retired, housework, unemployed, temporarily unable to work, permanently unable to work, other).
- Smoking habits (non-smoker, ex-smoker and smoker).
- Alcohol abuse (yes/no).

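### The two extraintestinal-manifestation response models name no covariate beyond disease type, so odds ratios meant to show impact may be confounded by age, gender and baseline activity, all of which are recorded.

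*SAP*

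**What the plan says.** **EIM models.** SAP 7.3 plans a logistic regression of lack of response in the induction phase. Its independent variables are "patient disease (CD or UC) and different extraintestinal manifestations variables", followed by a list of nine manifestations. A second model uses the same terms for loss of response in the maintenance phase ("We will repeat this analysis with the" other outcome). Section 7 of the protocol has no separate EIM analysis, so SAP 7.3 is the only specification.

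**Severity model.** SAP 7.3 first splits patients by baseline score: "We will classify the patients into IBD severe or non-severe at baseline based on the HBI and PMI scores". It then models severe against non-severe, where "patient disease (CD or UC) and different comorbidities variables will be used as independent variables". Protocol 7.6 asks for multivariable models but names no covariates.

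**Primary models, for contrast.** Protocol 7.4 plans two models for the same two response outcomes, "adjusting for sociodemographic and clinical profile of patients". SAP 7.2 repeats this.

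**What is recorded.** Protocol 6.1 lists "sociodemographic (age, gender, race, level of education, smoking habits alcohol intake" among the data to be collected. Protocol 6.4.4 adds "Disease activity at the beginning of the reference period and at the study visit through collection of the following variables", with PMS for UC and HBI for CD. Age enters the SAP only in the descriptive tables of section 5.2: "This analysis included the age of patients and number pack-year in smoking habits".

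**The concern.** The primary objective and the first secondary objective are worded alike: each asks for the impact of a patient profile on response to biologics. One is to be adjusted and the other is not, and no reason is given.

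Baseline activity matters most. SAP 7.1 defines non-response as failure to fall by at least 2 points from baseline in HBI or PMS. SAP 7.3 allows for patients with a baseline PMS of 0-1, which it classes as remission; for them a 2-point fall is arithmetically impossible. The starting score therefore helps to decide who counts as a non-responder. If patients with EIM start from different activity than patients without, the EIM odds ratio takes up part of that difference. Age and gender could act in the same way.

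A reader could then take as an effect of EIM on response something that only reflects who has EIM. Correcting the primary models would not help, because SAP 7.3 has its own list of terms. Copying the SAP 7.2 candidate list would not help either, since that list also lacks age and baseline activity.

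**Working it through.** **1. The plan's own figure.** Protocol 7.1 gives 10 events per variable, at most 10 variables and 50% non-response. N = 10 × 10 / 0.50 = 200 per disease, as stated. The EIM and severity models carry a disease-type term, so each pools 400 patients.

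**2. Could the omission matter?** The documents give no association between EIM and activity, or between activity and response, so this is an illustration on assumed values. Treat EIM as one yes/no variable with no true effect. Let half the patients have high baseline activity, EIM be present in 40% of the high and 20% of the low group, and non-response be 20% and 50%.
- Non-response with EIM: (0.5 × 0.4 × 0.2 + 0.5 × 0.2 × 0.5) / 0.30 = 0.09 / 0.30 = 30.0%
- Non-response without EIM: (0.5 × 0.6 × 0.2 + 0.5 × 0.8 × 0.5) / 0.70 = 0.26 / 0.70 = 37.1%
- Crude odds ratio: (0.300 / 0.700) / (0.371 / 0.629) = 0.73, where the true value is 1

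Overall non-response here is 0.09 + 0.26 = 35%, not the planned 50%. With other assumptions (a yes/no confounder with outcome odds ratio 1.5 to 3, present in 60% of patients with EIM and 40% of those without), the crude odds ratio is 1.08 to 1.24. With equal prevalence it is 1.00. Either direction is possible, and so is no bias.

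**3. Does the adjustment fit the sample?** Events per parameter = 400 × non-response rate / number of parameters. The 50% is from Protocol 7.1. The 30% is the upper figure for primary non-response in Protocol section 4.

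| Terms in the primary non-response model | Parameters | At 50% (200 events) | At 30% (120 events) |
|---|---|---|---|
| As planned: disease type + 9 EIM | 10 | 20.0 | 12.0 |
| + age, gender, activity as one term | 13 | 15.4 | 9.2 |
| + age, gender, activity in four categories (3 terms) | 15 | 13.3 | 8.0 |

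At 30%, 120 events allow 12 parameters. Merging manifestations to save one term (activity as one term) or three (four categories) restores the rule.

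For loss of response, assume 20% to 50% of 200 to 280 primary responders, that is 40 to 140 events. This gives 4.0 to 14.0 per parameter as planned and 3.1 to 10.8 with 13 parameters. At 60 events, 6 parameters are allowed: disease type, age, gender, activity and two EIM groups. At 40 events, those four terms and a single any-EIM indicator give 40 / 5 = 8.0. That is below the rule, but better than the 4.0 of the model as planned.

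**4. Severity model.** Disease type plus the 19 listed comorbidities is 20 parameters. The severe share is not given; at an assumed 10%, 20% or 30% there are 40, 80 or 120 events, or 2.0, 4.0 or 6.0 per parameter. Adding age and gender (22 parameters) gives 1.8, 3.6 or 5.5. With the comorbidities reduced to one term, the model has disease type, age, gender and comorbidity (4 parameters): 10.0, 20.0 or 30.0.

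An illustration for age, with no true effect: the oldest quarter has comorbidity in 30% against 6%, and severe disease in 20% against 10%.
- Severe with comorbidity: (0.25 × 0.30 × 0.20 + 0.75 × 0.06 × 0.10) / 0.12 = 16.25%
- Severe without: (0.25 × 0.70 × 0.20 + 0.75 × 0.94 × 0.10) / 0.88 = 11.99%
- Crude odds ratio: 1.42. If severe disease is instead 7% against 12%, it is 0.79.

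**The case against.** **No bias is shown.** Every input to the illustrations is assumed, and the severity example changes direction with its inputs. This stands. A reader might infer that the planned odds ratios are confounded; the documents support only that they may be. The illustration also reduces nine jointly fitted manifestations to one variable. Because the manifestations are entered together, they do adjust for each other; what is missing is any covariate beyond them and disease type.

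**Baseline activity and the severity model.** A reader might extend the point about baseline activity to all three models. That fails: baseline HBI or PMS defines the outcome of the severity model and cannot also confound it.

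**The study is exploratory.** SAP 5.1 calls it descriptive, and the severity objective asks for a profile. A profile that partly reflects age is still the profile, so unadjusted odds ratios are defensible there if labelled as such. The argument does not carry over to the EIM objective, which asks for impact.

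**Adjustment costs events.** This stands against adding everything recorded. With smoking (2 terms) and disease duration as well, the EIM model has 16 parameters: 200 / 16 = 12.5 events each at 50% and 120 / 16 = 7.5 at 30%. The severity model with age, gender, smoking and duration would have 25; at 12.5% severe (50 events) that is 2.0 each. A short covariate list is the answer, with grouping.

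**Data problems.** SAP 7.1 foresees unavailable indexes, and complete-case fitting on the baseline score would drop those patients. HBI and PMS are different scales in a pooled model. Protocol 6.4.4 gives no date for EIM, so its order relative to baseline activity is unknown. The first two need rules; the third is a reason to show the model without covariates as well.

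**Conclusion.** The point holds for the two EIM response models. Their terms are fixed in SAP 7.3 without age, gender or baseline activity, although the objective is impact, the data are collected, and the starting score partly determines the outcome. The odds ratios may be confounded. The size and direction cannot be computed from the documents; 0.73 under no true effect shows only that a material distortion is possible under assumed values.

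For the severity model the point is smaller: age and gender are absent, baseline activity is not an omission, and a clear label is an acceptable alternative to adjustment.

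The events-per-parameter results assume 400 analysed patients, 30% to 50% primary non-response, 20% to 50% loss of response among primary responders, and a severe share of 10% to 30%. The last two ranges are not in the documents.

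**What to change.** In SAP 7.3, before database lock:

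- **EIM models.** Prespecify age at biologic start, gender and baseline activity in both models. Age at start follows from recorded age and the recorded start date of the biologic.
- **Scale.** Enter activity in a form that pools HBI with PMS: the SAP's own remission, mild, moderate and severe classes, or the score standardised within disease.
- **Missing index.** State a rule that keeps these patients in the model. One option is the physician's global assessment, which Protocol 6.4.4 lists with the disease-activity items in four similar classes.
- **Grouping.** Merge rare manifestations, by a rule set without reference to outcome, to keep 10 events per parameter. Allow more grouping for loss of response. If its events are too few even for a single any-EIM term, say so and treat the model as descriptive.
- **Reporting.** Show the odds ratios without covariates next to the adjusted ones.
- **Severity model.** Add age and gender and replace the 19 indicators by a grouped term such as the Charlson score or any comorbidity. Otherwise, label the odds ratios as unadjusted associations.

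The change is to SAP wording and needs no new data. It costs a few degrees of freedom and some detail on individual rare manifestations or comorbidities.
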